##### 9.4.1 Primary efficacy analysis

The primary efficacy endpoint is the change in serum levels of TSH at the end of the 12-week treatment period with Tirosint® capsules vs baseline.

A mixed model ANCOVA repeated measures model will be used to test differences in means of TSH level at Visit 4 vs baseline visit. As covariates will be considered the following baseline variables: Age, Sex, BMI and the prescribed Tirosint® dosage (dose/Kg). Unstructured covariance structure will be used (If a different type of covariance structure will be used details will be provided).

Normal distribution for the TSH data will be tested with Shapiro Wilks.

If TSH data results not to be distributed as a normal distribution the following methods will be applied:

- Data will be log transformed and analyzed with the ANCOVA repeated measures model described above.

The TSH level at each time point will also be summarized as continuous variable.

The primary efficacy analysis will be performed on data with missing values replaced with LOCF method and on original data (values recorded after changes in LT4 dose will not be considered in either case).

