Tirosint® will be taken as a single daily dose in the morning, on an empty stomach, one-half to one hour before breakfast, according to labelling. All subjects will separate their LT4 by at least 4 hours from any drug known to interfere with LT4 absorption (e.g. iron and calcium supplements, see section 6.5) and by at least 1 hour from foods that are known to interfere with LT4 absorption.

The patients will continue intake of PPI according to their individual prescription and habits.

Patients will remain on their pre-screening dose (both for LT4 and for PPI) throughout the whole study duration.

No LT4 dose adjustments will be allowed during the whole study, unless TSH levels > 10 or < 0.01 mIU/L are measured, which require immediate dose adjustment of LT4. In particular:

- If TSH levels > 10 or < 0.01 mIU/L are measured during the baseline visit the subject will drop-out, because pre- and post-switch comparisons at the same dose would not be possible.
- If TSH levels > 10 or < 0.01 mIU/L are measured during control visits (interim or unforeseen), the dose will be adjusted and the subject will remain in the study. To the purpose of the efficacy evaluation in such cases reference is made to section 11.3.

The Investigator can adjust the LT4 dose for a patient with TSH levels < 10 or ≥ 0.01 mIU/L, if this is considered necessary for the safety of a patient. The reason should be appropriately documented.

Changes in the dose of PPI are acceptable during the study provided that the dose remains ≥ 20 mg/day for omeprazole, esomeprazole and rabeprazole, ≥ 15 mg/day for lansoprazole, ≥ 30 mg/day for dexlansoprazole, and ≥ 40 mg/day for pantoprazole. If the newly prescribed dose falls outside this range or if the therapy with PPI is interrupted, the subject will drop out of the study.

Any changes will be described in the CRF.

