## 2 VERSION HISTORY

Version Number	Summary/Reason for changes	Date Issued
Draft 1.0	Draft specification based on the Clinical Study Protocol (Version 6.0, 17 June 2019), CRF (Version 3.0 – 05 November 2018) and Patient’s Diary (Version 2.0 – 20 July 2018).	13/09/2021
Draft 2.0	Internal review. Added overall compliance tables and Daily dosage; Splitted the secondary efficacy endpoint models on laboratory data; Modified the mITT definition.	15/10/2021
Draft 3.0	Primary and secondary analysis will be repeated on original data. Added details on model covariance structure.	10/11/2021
Final 1.0	First final version release.	06/12/2021
Final 2.0	The baseline value covariates will not be included in the repeated measures models.	23/12/2021

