#### Baseline covariates

Since the repeated measures analysis will be performed only on two time points (one baseline and one post baseline), the models will not include the basal value also as additional covariate for the analysis.

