## 7 VARIABLES OF INTEREST

### 7.1 EFFICACY VARIABLES

#### 7.1.1 Primary efficacy variables

The primary efficacy variable is the serum levels of TSH.

Serum levels of TSH will be measured at screening visit(s), at baseline, halfway through the treatment period and at the final visit.

The serum levels of TSH recorded after changes in LT4 dose will not be considered for the analysis.

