## 8 HANDLING OF MISSING AND INCOMPLETE DATA

Cases of withdrawal from the study, for any reasons, after inclusion will not be replaced. However, the withdrawn cases will be analyzed in the ITT analysis.

TSH, FT4, TT4, FT3, TT3, CPK, SHBG, ferritin, ACE level, and lipid panel (TC, HDL-C, LDL-C, VLDL-C, TG) values recorded after changes in LT4 dose will not be considered for the statistical analysis.

For analyses that require complete patient data, missing values during the treatment period will be replaced, for all primary and secondary variables, with the Last Observation Carried Forward (LOCF) technique. Imputed values will be included in the analysis set(s), but will not change the original clinical database.

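### The primary TSH model leaves out Visit 3, the value that can lead to a dose change and loss of Visit 4; the bias is probably small, and adding the visit is cheap (minor)

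*SAP*

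**What the plan says.** **Model.** SAP 9.4.1: "A mixed model ANCOVA repeated measures model will be used to test differences in means of TSH level at Visit 4 vs baseline visit". SAP 4 (Changes from study protocol, Baseline covariates) confirms that "the repeated measures analysis will be performed only on two time points (one baseline and one post baseline". Visit 3 TSH has its own secondary model in SAP 9.4.2.

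**Dose changes.** Protocol 6.2 sets limits of 10 and 0.01 mIU/L. When values beyond them "are measured during control visits (interim or unforeseen), the dose will be adjusted and the subject will remain in the study". Inside the limits the investigator may also change the dose "if this is considered necessary for the safety of a patient"; no numerical threshold is given.

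**Excluded values.** SAP 7.1.1: "The serum levels of TSH recorded after changes in LT4 dose will not be considered for the analysis". SAP 8 repeats this and says that "missing values during the treatment period will be replaced, for all primary and secondary variables, with the Last Observation Carried Forward (LOCF) technique" where an analysis needs complete data.

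**Two runs.** The primary analysis is "performed on data with missing values replaced with LOCF method and on original data", and both runs leave out values after a dose change. Neither is named as primary. The version history has only "Primary and secondary analysis will be repeated on original data".

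**Likelihood methods.** Protocol 11.3.3 allows a maximum-likelihood sensitivity analysis, to be described in the SAP. SAP 8 describes none.

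**The concern.** Visit 4 can be lost because of a TSH value that was measured and recorded. The original-data run omits that value, so it treats the loss as if it depended on Visit 2 and the covariates alone. The LOCF run uses it, but as a stand-in for Visit 4, although an extreme value tends to move back towards the patient's usual level.

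If most changes follow high TSH and TSH is otherwise stable, the two runs err in opposite directions. Low triggers reverse both signs, and balanced triggers roughly cancel. The contrast affected is the primary one, and no rule chooses between the runs if they differ.

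The modified ITT set (SAP 6.4) does not remove this. It requires valid Visit 2 and Visit 3 TSH on the same dose, and a patient adjusted after Visit 3 meets that.

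**Working it through.** **1. The plan's own figures.** Protocol 11.3.1 gives n = 48, difference 0.7, SD of differences 1.9, two-sided 0.05 and 70% power. The exact paired t-test gives 70.5%, so the figure is reproduced. The allowance also reproduces: 48 / (1 − 0.20) = 60. That 20% covers drop-out and dose adjustment together, and it is the only figure in the documents that bears on the number of changes. SAP 4.1 reports 47 included and 45 completed. The 45 does not bound the loss, because a patient can complete after a dose change and still have no usable Visit 4 TSH.

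**2. Form of the bias.** Let Y2, Y3 and Y4 be log TSH on an unchanged dose, R = 1 if the dose changes after Visit 3, and p = P(R = 1). The target is E(Y4) − E(Y2).

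- LOCF: bias = p × E(Y3 − Y4 | R = 1).
- Two-visit likelihood: bias = p × E(m(Y2) − Y4 | R = 1), where m is the regression of Y4 on Y2 among unchanged patients.
- Three-visit likelihood: the same with m(Y2, Y3). It is zero when R depends only on Y2 and Y3 and the regression is linear.

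**3. Assumptions (none from the documents except the eligibility and dose limits).** Median TSH 1.5 or 1.8 mIU/L; on the log scale, between-patient SD 0.55 and within-patient SD 0.57 (independent errors) or 0.62 (autocorrelation 0.4). Screening TSH is 0.3 to 4.0 and baseline TSH 0.01 to 10. The listed covariates are not simulated. The raw SD of Visit 4 minus Visit 2 comes out at 1.7 to 2.0, close to the planning value of 1.9.

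**4. Results (bias in log TSH, Visit 4 minus Visit 2).**

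| Dose changes at Visit 3 | Adjusted | Original data, two visits | LOCF |
|---|---|---|---|
| Mandatory limits only | 0.4–0.8% | −0.002 to −0.006 | +0.004 to +0.009 |
| All above 10 and a quarter of those above 4.0 | 2.4–3.5% | −0.009 to −0.019 | +0.014 to +0.028 |
| Highest 5% (cut about 4.8–5.6) | 5% | −0.020 to −0.032 | +0.029 to +0.046 |
| Same cut, true log shift −0.5 (raw fall 0.62–0.78) | 1% | −0.005 to −0.008 | +0.008 to +0.012 |

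The first three rows assume no treatment effect; in them the three-visit model's bias is at most 0.001. With the mandatory limits alone, 70–82% of trials of 47 have no affected patient.

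**5. Size of the 5% case.** It means 0.05 × 47 = 2.35 patients. Relative to the standard error, the largest biases are 0.032 / 0.12 = 0.27 (two-visit) and 0.046 / 0.12 = 0.38 (LOCF). As ratios, exp(−0.032) = 0.97 and exp(0.046) = 1.05. The 95% interval misses the truth in 5.2–5.6% of trials (two-visit), 5.6–7.2% (LOCF) and 4.6–4.9% (three-visit). Over 10,000 trials the Monte Carlo error is √(0.05 × 0.95 / 10,000) = 0.2 points, so 5.2% cannot be told from 5%.

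**6. Where the three-visit model falls short.**

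- *Unforeseen visits.* If all 5% are triggered between Visits 3 and 4, it keeps −0.014 to −0.028 (two-visit −0.020 to −0.048).
- *Other information.* If the trigger also carries information about later TSH (assumed weight 30–50%), it keeps −0.021 to −0.042 (two-visit −0.041 to −0.059).
- *Raw scale.* A second set of assumptions has median 1.6, log correlation 0.5 or 0.7 and spread set to a raw SD of differences of about 1.9. With the highest 20% changed, the three-visit bias is at most 0.003 on the log scale but +0.11 to +0.14 mIU/L on the raw scale, because raw TSH is skewed.

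**The case against.** The case against acting is strong on size. With the mandatory limits the effect is negligible. Under a fall of the planned size few patients cross the cut and the bias nearly vanishes. Much is visible already: SAP 9.4.2 reports how many patients change dose and the change in dose per kg, SAP 9.5.1 counts low, normal and high values by visit, and the Visit 3 model is untouched by changes made after that visit. If triggers run mostly one way and TSH is stable, the two runs bracket the same-dose value. Protocol 11.3.3 puts LOCF first and likelihood methods as optional. The SAP was drafted in 2021 and reports early termination of an open-label trial, so replacing the primary estimator then has a pre-specification cost. All of this stands, and it limits the point to a minor one.

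It does not remove the point. Bracketing depends on one-directional triggers, and the plan does not say which of the two runs counts.

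A reader might infer more than the documents support:

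- *That the primary result is materially biased.* No count of dose changes is given, and discretionary use is unknown.
- *That 20% of patients are adjusted.* That figure is a planning allowance that also includes drop-out.
- *That LOCF is the primary run.* The version-history line hints at it, but SAP 9.4.1 does not say so.
- *That a third visit cures the problem.* Discretion under Protocol 6.2 may rest on information other than TSH at Visits 2 and 3.

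**Conclusion.** The gap is real and minor. The two-visit model ignores a measured value on which loss of Visit 4 can depend, and LOCF carries that value forward.

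Under the assumptions above, neither run is off by more than 0.009 log units with mandatory changes alone. With 5% adjusted for high TSH and no treatment effect, the bias stays below 0.4 of a standard error in either run; with a true fall near 0.7 mIU/L it is about 0.1 of one or less (0.012 / 0.12 = 0.10). Larger biases need broad discretionary adjustment, which the documents do not show. The signs assume mostly high triggers and stable TSH from Visit 3 to Visit 4. The structure is certain from the text; the size rests on assumption. The case for a change is that it costs little and concerns the primary contrast.

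**What to change.** **SAP 9.4.1.** Fit the likelihood repeated-measures model to TSH at Visits 2, 3 and 4: visit as a factor, unstructured covariance, the covariates already listed, and values after a dose change set to missing. Report its Visit 4 minus Visit 2 contrast in place of the two-visit original-data fit. Keep LOCF as planned, and state which run is primary. Reword the two-time-point statement in SAP 4 to match.

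**At the least,** add the three-visit model to SAP 8 as the maximum-likelihood sensitivity analysis that Protocol 11.3.3 foresees.

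**Scale.** Keep the existing log-transform rule, and note that the correction works fully only on the log scale.

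**Limit to state.** The model removes the bias only when the dose change depends on Visit 2 and Visit 3 TSH. Triggers at unforeseen visits, or discretionary changes based on other information, can leave half or more of it.

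**Cost.** SAP wording and a small programming change; the data are already collected. With complete data the contrast is identical to the two-visit one, and at 5% adjusted and n = 47 its standard error is within 1%. If the three-visit model is made primary, that departs from the protocol's LOCF-first order late in an open-label trial and should be recorded as a change from protocol.

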##### 9.4.2 Secondary efficacy analysis

- Serum levels of FT4, FT3, TT4, TT3, CPK, SHBG, ferritin, ACE level, and lipid panel (TC, HDL-C, LDL-C, VLDL-C, TG) at the end of each 12-week treatment period vs baseline

The secondary efficacy endpoints are the changes in serum levels of FT4, FT3, TT4, TT3, CPK, SHBG, ferritin, ACE level, and lipid panel (TC, HDL-C, LDL-C, VLDL-C, TG) at the end of each 12-week treatment period with Tirosint® capsules vs baseline.

Mixed model ANCOVA repeated measures models will be used to test differences in means of serum levels of FT4, FT3, TT4, TT3, CPK, SHBG, ferritin, ACE level, at Visit 4 vs baseline visit. As covariates will be considered the following baseline variables: Age, Sex, BMI and the prescribed Tirosint® dosage (dose/Kg). Unstructured covariance structure will be used (If a different type of covariance structure will be used details will be provided).

Normal distributions for each serum level data will be tested with Shapiro Wilks. If data results not to be distributed as a normal distribution the following methods will be applied:

- Data will be log transformed and analyzed with the ANCOVA repeated measures models described above.

- The change in serum levels of TSH, FT4, FT3, TT3 at Visit 3 vs baseline

Mixed model ANCOVA repeated measures models will be used to test differences in means of serum levels of TSH, FT4, FT3, and TT3 at Visit 3 vs baseline visit. As covariates will be considered the following baseline variables: Age, Sex, BMI and the prescribed Tirosint® dosage (dose/Kg). Unstructured covariance structure will be used (If a different type of covariance structure will be used details will be provided).

Normal distributions for each serum level data will be tested with Shapiro Wilks. If data results not to be distributed as a normal distribution the following methods will be applied:

- Data will be log transformed and analyzed with the ANCOVA repeated measures models described above.

The serum levels of TSH, FT4, FT3, TT4, TT3, CPK, SHBG, ferritin, ACE level, and lipid panel at each time point will also be summarized as continuous variables.

- LT4 dose adjustment

Frequencies and percentages of patients requiring changes in LT4 daily dose during the treatment period will be provided.

Changes in mean LT4 daily dose/kg at the end of the treatment period versus baseline will be analyzed by a mixed model ANCOVA repeated measures model with LT4 daily dose/kg at each time point as dependent variable. Unstructured covariance structure will be used (If a different type of covariance structure will be used details will be provided).

Normal distribution for the LT4 daily dose/kg data will be tested with Shapiro Wilks.

If LT4 daily dose/kg data results not to be distributed as a normal distribution the following methods will be applied:

- Data will be log transformed and analyzed with the ANCOVA repeated measures model described above.

The secondary efficacy analysis will be performed on data with missing values replaced with LOCF method and on original data (values recorded after changes in LT4 dose will not be considered in either case).

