**Secondary end-points:**

*Efficacy assessments:*

Change in serum levels of FT4, TT4, FT3, TT3, CPK, SHBG, ferritin, ACE level, and lipid panel at the end of the 12-week Tirosint® treatment period with respect to its baseline.

Serum levels of TSH, FT4, FT3 and TT3 halfway through each treatment cycle.

LT4 dose adjustment evaluated both in terms of number of patients requiring changes in daily dose during the treatment period and as mean change in daily LT4 dose at the end of the treatment period versus the baseline.

*Safety assessments:*

Adverse events

Vital signs

Body weight

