**Statistical analysis:**

*Primary Efficacy Analysis*

The primary efficacy end-point will be the change in serum levels of TSH at the end of the 12-week treatment period with Tirosint® capsules with respect to baseline.

The serum levels of TSH will be analyzed by means of a repeated measures analysis of covariance on the difference (final vs baseline visit) with basal value as covariate. The 95% confidence interval will be calculated. Additional non-parametric analyses may be performed on the evolution of TSH serum levels as sensitivity analyses.

Baseline variables (e.g. gender, pre-study LT4 product, LT4 dose, proton pump inhibitor product and dose, etc.) may also be used as covariates if appropriate.

The serum levels of TSH recorded after changes in LT4 dose will not be considered for the analysis.

*Secondary Efficacy Analyses*

The secondary efficacy end-points will be the change in

serum levels of FT4, TT4, FT3, TT3, CPK, SHBG, ferritin, ACE level, and lipid panel at the end of each 12-week treatment period with Tirosint® capsules with respect to baseline. The change in serum levels of TSH, FT4, FT3, TT3 at Visit 3 with respect to baseline will also be analyzed as secondary efficacy end-points.

Serum levels of FT4, TT4, FT3, TT3, CPK, SHBG, ferritin, ACE level, and lipid panel (TC, HDL-C, LDL-C, VLDL-C, TG) will be analyzed by means of a repeated measures analysis of covariance with basal value as covariate.

The 95% confidence interval will be calculated.

Baseline variables (e.g. gender, pre-study LT4 product, LT4 dose, proton pump inhibitor product and dose, etc.) may also be used as covariates if appropriate.

The secondary end-point parameters recorded after changes in LT4 dose will not be considered for the analysis.

The dose adjustment evaluated in terms of number of patients requiring changes in LT4 daily dose during the treatment period will be described using frequencies and percentages.

Changes in mean LT4 daily dose at the end of the treatment period versus baseline will be analyzed by means of a repeated measure analysis of variance model.

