### **3.2 Secondary objective(s)**

The secondary objectives of this study are to evaluate any biochemical changes in creatine phosphokinase (CPK), sex hormone binding globulin (SHBG), ferritin, angiotensin converting enzyme (ACE) level, and lipid panel, as well as the change in daily LT4 dose in the same population upon switch from conventional tablets to Tirosint capsules.

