## **9.2 Secondary Efficacy variables**

The secondary efficacy variables will be the serum levels of FT4, TT4, FT3, TT3, CPK, SHBG, ferritin, ACE level, and lipid panel.

Serum levels of FT4, FT3 and TT3 will be measured at screening visit, at baseline, halfway through the treatment period and at the final visit. In addition, serum levels of TT4, CPK, SHBG, ferritin, ACE level, and lipid panel (TC, HDL-C, LDL-C, VLDL-C, TG) will be measured at baseline and at the end of the 12-week treatment period (Final visit).

LT4 dose adjustment will be evaluated both in terms of number of patients requiring changes in daily dose during the treatment period and as mean change in daily LT4 dose at the end of the treatment period versus baseline.

Please refer to section [9.1](#) for methodological details.

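### SAP 9.4.2 tests the LT4-dose endpoint in mcg/kg although it is defined as daily dose, without declaring the switch, naming the weight visit, or limiting the exclusion to laboratory values

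*SAP*

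**What the plan says.** **Definition.** The protocol synopsis lists, among the secondary endpoints, "mean change in daily LT4 dose at the end of the treatment period versus the baseline". Protocol 9.2 repeats it ("mean change in daily LT4 dose at the end of the treatment period versus baseline"), protocol 11.3.6 plans a repeated-measures ANOVA of mean daily dose, and SAP 7.1.2 keeps the same definition. None of these scales by body weight. Protocol 3.2 makes it a secondary objective to evaluate the "change in daily LT4 dose in the same population upon switch from conventional tablets" to the capsules, and SAP 3.2 carries that over.

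**Analysis.** SAP 9.4.2 states: "Changes in mean LT4 daily dose/kg at the end of the treatment period versus baseline will be analyzed by a mixed model ANCOVA", using a repeated-measures model "with LT4 daily dose/kg at each time point as dependent variable". There is also a log-transform route: "If LT4 daily dose/kg data results not to be distributed as a normal distribution the following methods will be applied". SAP section 5 defines daily dosage in mcg and daily dosage per body weight as two separate variables, and only the second is modelled. Its divisor is a weight with no visit attached. SAP 7.2 schedules weight at screening, baseline and the final visit.

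**Declared changes.** *Changes from study protocol* in SAP section 4 covers compliance, the added mITT set and the dropped baseline covariate. The change of scale is not there.

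**Exclusion.** SAP 9.4.2 closes by saying the secondary analysis will be run with LOCF and on "original data (values recorded after changes in LT4 dose will not be considered in either case". SAP 7.1.2, SAP 8 and protocol 11.3.3 confine the same rule to named laboratory analytes. The protocol synopsis does not expressly do so: "The secondary end-point parameters recorded after changes in LT4 dose will not be considered for the analysis".

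**The concern.** This model is the only inferential test of a stated secondary objective, and it does not test the variable the objective names. Because the SAP defines the mcg and mcg/kg variables separately, the per-kg wording cannot be read as shorthand for daily dose.

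Dose/kg is a ratio. If each visit uses its own weight, which is the ordinary reading of a dependent variable taken at each time point, the endpoint moves whenever weight moves. The test could then report a dose change when no dose changed, or miss one that occurred. The two effects may also pull in opposite directions. Protocol 2.1 lists weight gain as a feature of hypothyroidism, so if the capsule is better absorbed, weight would if anything fall. That raises mcg/kg, while any dose reductions lower it. This is an inference, and its size is unknown.

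The exclusion wording adds a second problem. Post-adjustment doses are what the endpoint measures. If they are dropped and then filled by LOCF, which SAP 8 applies to all secondary variables, the change in dose disappears.

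**Working it through.** **The plan's own figure.** The documents give no power or precision for the dose endpoint. Their only computable figure is for TSH: n = 48, difference 0.7, SD of differences 1.9, two-sided 0.05. The noncentral t distribution gives 70.5% against the stated 70%, and 48/(1 − 0.20) = 60. Both reproduce, but neither bears on this point.

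**Inputs.** The 45 completers come from SAP 4.1. Numbers of dose changes, 25 mcg steps, body weights and weight changes are all assumed. The nearest figure in the documents is the planning rate of about 20% for drop-out and dose adjustment combined; 0.20 × 45 = 9 patients.

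**Step 1: weight alone.** At an unchanged dose D, losing 1 kg from weight W changes dose/kg by D/(W − 1) − D/W.

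| Dose | Weight | Change in dose/kg |
|---|---|---|
| 125 mcg | 80 kg | 125/79 − 125/80 = +0.0198 (× 80 = 1.58 mcg) |
| 88 mcg | 100 kg | 88/99 − 88/100 = +0.0089 |
| 250 mcg | 60 kg | 250/59 − 250/60 = +0.0706 |

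With baseline weight at both visits the change is 0 in every row, so the unnamed visit decides the result.

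**Step 2: the endpoint as defined.** Paired change in mcg, n = 45:

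- 5 patients cut by 25 mcg: mean −125/45 = −2.78; SD = √[(5 × 625 − 45 × 2.78²)/44] = 7.95; t = −2.78/(7.95/√45) = −2.35; p = 0.024; 95% CI −5.16 to −0.39.
- 9 cut: mean −225/45 = −5.0, p = 0.0018.
- 4 cut and 1 raised: mean −75/45 = −1.67, p = 0.183.

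**Step 3: simulation of the per-kg test.** Doses are drawn from strengths of 88–200 mcg, weight is N(80, 16) kg floored at 45 kg, and weight change is normal. The test is a paired t-test on dose/kg (the two-time-point model without covariates). Data are logged when Shapiro-Wilk rejects normality of baseline dose/kg, which happens in about 72% of trials. There were 2,000 trials per cell with no dose change and 3,000 otherwise. Entries are the percentage of trials significant at 0.05.

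| Scenario, visit-specific weights | SD of weight change 0.5 kg | 1.0 kg | 1.5 kg | 2.5 kg | 3.5 kg |
|---|---|---|---|---|---|
| No dose change, mean loss 1 kg | – | 100 | 99.0 | 75.7 | 50.9 |
| No dose change, mean loss 0.5 kg | – | 88.6 | 56.0 | 27.4 | 19.0 |
| No dose change, no mean loss | – | 5.1 | 5.8 | 5.2 | 4.8 |
| 5 cut, no mean loss | 98.4 | 83.1 | 67.8 | 46.6 | 35.0 |
| 9 cut, no mean loss | 100 | 100 | 100 | 98.1 | 90.7 |
| 4 cut and 1 raised, no mean loss | 0 | 0.9 | 1.7 | 5.7 | 6.0 |

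In the first three rows the mcg change is exactly 0. With baseline weight at both visits, the 5-cut and 9-cut scenarios are significant in 100% of trials and the mixed one in 0%.

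The opposing directions also show up. With 5 cut and SD 2.5 kg, the mean estimate is −0.034 mcg/kg at no mean weight change. It shrinks to −0.010 with a mean loss of 1 kg, and only 0.7% of trials are then significant.

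**Step 4: literal exclusion.** Post-change doses are dropped, then left missing or replaced by the pre-change dose. With baseline weight at both visits every change is exactly 0 and there is nothing to test. With visit-specific weights and no mean weight change, the test is significant in 4.4% to 5.6% of trials whatever the doses did.

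**The case against.** - **The exclusion was probably meant for laboratory values.** SAP 7.1.2, SAP 8 and protocol 11.3.3 say so, and the literal reading would empty an endpoint that Amendment 2 added to capture dose changes. This is fair. What remains is an inconsistency inside the SAP that one phrase would resolve, not evidence that doses will be dropped.
- **A weight-driven result would be visible.** The report will also give the count of adjusted patients (SAP 9.4.2), mean dose in mcg (SAP 9.5.4) and weight change with a confidence interval (SAP 9.5.3). That helps an attentive reader, but none of these outputs tests the endpoint as defined.
- **The false-signal rates assume a mean weight loss.** This stands. Patients enter with TSH of 0.3 to 4.0 mIU/L and switch at the same dose, the documents give no expected weight change, and with none the rate is about 5%.
- **The power loss depends on the scenario.** With 9 cut, in line with the planning rate, the per-kg test is significant in about 91% or more. With mixed directions mcg gains nothing. With 5 identical cuts among 40 zeros, an exact sign-flip test gives 2/2⁵ = 0.0625, so the t-test's p = 0.024 is itself fragile, and a mcg model has the same zero-heavy data.
- **Dose/kg is a legitimate scale.** Protocol 2.1 describes starting doses by body weight and the SAP uses dose/kg as a covariate. That could justify a declared change of scale, but not an undeclared one.

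**Conclusion.** The concern holds in each of its parts. The modelled variable differs from the defined endpoint, the switch is not declared, the weight visit is not named, and the closing exclusion lacks the laboratory-only limit found elsewhere. These are textual facts and need no assumption.

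The numerical consequence is conditional. The 1.6 mcg equivalent per kg lost is arithmetic at an assumed 125 mcg and 80 kg. The significance rates rest on assumed weight changes and numbers of adjustments, and range from negligible to near certain. The consequence is confined to one secondary test in a study the protocol calls a pilot. It should be corrected because that test is the only one for a stated objective and the correction is cheap.

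**What to change.** 1. **SAP 9.4.2, scale.** Make the change in daily dose in mcg, as already defined in SAP section 5, the main model. Keep mcg/kg as a supportive analysis with baseline weight at both visits, and name that weight in section 5. If mcg/kg stays the modelled scale, list it under *Changes from study protocol*.
2. **SAP 9.4.2, exclusion.** Limit the closing exclusion to the laboratory analytes named in SAP 7.1.2 and SAP 8, and state that the protocol synopsis sentence is read the same way.
3. **SAP 9.4.2 and SAP 8, dose data.** State that recorded LT4 doses through Visit 4, including those after an adjustment, enter the dose analysis and are not replaced by the pre-change dose under LOCF. For patients who leave before Visit 4, carry forward the last recorded dose, including any adjustment.

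The cost is a few sentences, plus one line in the list of changes if mcg/kg is kept. Doses and weights are already collected. If the SAP is closed, its introduction allows a deviation to be explained in the statistical report.
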